3.5.2. Exposure

Human exposures have been estimated from the pharmacokinetics in the cynomolgus monkey since a non-human primate represents the most closely related species. Approximately dose-proportional exposure was seen in the 13-week toxicity study (Covance study no. 8355565) and ¹⁴C pharmacokinetic study (Covance study no. 8355568) over a dose range of approximately 1.1 to 100 nmol/kg (5.06 to 462.29 µg/kg)⁴. However, the lowest dose (5.06 µg/kg) from the ¹⁴C study has been used to estimate the human exposures as it is closest to the proposed human dose range and has the sufficient quantifiable data.

The assumptions made in the human exposure estimation were that human exposure would be similar to the cynomolgus monkey and that exposure would be linear with dose. Following a dose of 5.06 µg/kg in the cynomolgus monkey, the C_{max} was 1.96 ng/mL and AUC_{0-∞} was 12.7 ng.h/mL. The extrapolated exposures at the planned human doses are shown in [Table 1](#) with margins calculated to the exposures at the NOAEL in the female rat.

Table 1: Estimated Human Exposure and Safety Margins to the NOAEL in the Female Rat for Single Dose Administration of OLP-1002

Human dose		Single dose to human		Safety margins for single dose	
(µg)	(µg/kg)	Predicted C _{max} (ng/mL)	Predicted AUC _{0-∞} (ng.h/mL)	Margin to C _{max}	Margin to AUC _{0-∞}
0.03	0.000500	0.000194	0.00125	129000	102000
0.12	0.00200	0.000775	0.00502	32100	25500
0.4	0.00667	0.00258	0.0167	9640	7650
1.2	0.0200	0.0077	0.0502	3210	2550
3	0.0500	0.0194	0.125	1290	1020
6	0.100	0.0387	0.251	643	510
12	0.200	0.0775	0.502	321	255
20	0.333	0.129	0.837	193	153
40	0.667	0.258	1.673	96	76
80	1.333	0.516	3.347	48	38
160	2.667	1.033	6.693	24	19

Abbreviations: AUC_{0-∞} = area under the plasma concentration-time curve extrapolated to infinity; C_{max} = maximum observed plasma concentration.

The dosing interval currently anticipated for the multiple-ascending-dose part of this study is 72 hours or 96 hours. Thus the average dosing interval (82 hours) is similar to the half-life determined in the monkey ¹⁴C study of 84 hours. Dosing at approximately once per half-life would be anticipated to result in accumulation of around 2-fold. However, higher levels of accumulation were observed (2.28-fold for C_{max} and 3.76-fold for AUC₀₋₂₄) on Day 88 at the top dose group (100 nmol/kg, 462.28 µg/kg) in the 13-week cynomolgus monkey toxicity study following twice-weekly dosing (every 72 or 96 hours). Calculations were performed to estimate the likely human half-life using a standard 1-point allometric approach from the ¹⁴C cynomolgus monkey pharmacokinetic study data. The exponents used were 0.75 for apparent total plasma clearance (CL/F) and 1 for apparent volume of distribution (V_z/F) values combined with the average body weight of the animal (3.1 kg) and scaling to a 60 kg human⁹⁻¹¹. This resulted in a human half-life estimate of 180 h which in turn gave an accumulation

estimate of 3.7-fold based upon a dosing interval of 82 h. This further supports the use of the greater than 2-fold accumulation from the 13-week cynomolgus study to estimate exposure following multiple dosing. Multiplication of the exposure estimates for the single ascending dose by 2.28 for C_{max} and 3.76 for AUC resulted in exposure estimates for multiple dosing presented in [Table 2](#).

Table 2: Estimated Human Exposure and Safety Margin to the NOAEL in the Female Rat for Multiple Dose Administration of OLP-1002

Human dose		Multiple dose to human		Safety margins for multiple dose	
(μg)	($\mu\text{g}/\text{kg}$)	Predicted C_{max} (ng/mL)	Predicted $AUC_{0-\infty}$ (ng.h/mL)	Margin to C_{max}	Margin to $AUC_{0-\tau,ss}$
0.03	0.000500	0.000442	0.00472	56000	27000
0.12	0.00200	0.00177	0.0189	14100	6800
0.4	0.00667	0.00589	0.0629	4230	2030
1.2	0.0200	0.017663	0.189	1410	680
3	0.0500	0.0442	0.472	560	270
6	0.100	0.0883	0.944	282	136
12	0.200	0.177	1.89	141	68
20	0.333	0.294	3.15	85	41
30	0.500	0.442	4.72	56	27
40	0.667	0.589	6.29	42	20

Abbreviations: $AUC_{0-\infty}$ = area under the plasma concentration-time curve extrapolated to infinity; C_{max} = maximum observed plasma concentration.

3.5.3. Proposed Doses

The proposed IMP dose levels for Parts A and B are shown in [Table 3](#).

Table 3: Proposed Investigational Medicinal Product Dose Levels for Parts A and B

Study Part	Group	Dose (OLP-1002)
Part A	A1	30 ng or placebo
	A2	120 ng or placebo
	A3	400 ng or placebo
	A4	1.2 µg or placebo
	A5	3 µg or placebo
	A6	6 µg or placebo
	A7	12 µg or placebo
	A8	20 µg or placebo
	A9	40 µg or placebo
	A10	80 µg or placebo
	A11	160 µg or placebo
Part B	B1	TBC or placebo
	B2	TBC or placebo
	B3	TBC or placebo
	B4	TBC or placebo
	B5*	TBC or placebo
	B6*	TBC or placebo

Abbreviations: TBC = to be confirmed
* groups to be included if required.

In Parts A and B, there should not be an increase of > 3-fold between dose levels above 120 ng.

Since predictions of human exposure of OLP-1002 suggest that OLP-1002 concentrations may not be quantifiable and human data have been estimated from a single species, it is proposed that the highest dose in the multiple-ascending-dose part will be up to 50% of the highest dose in the single-ascending-dose part (ie, if the highest dose in the single-ascending-dose part is 160 µg, the highest dose in the multiple-ascending-dose part will be 80 µg). Therefore, if the predicted accumulation of 3.7-fold occurs, the highest exposure in Part B will not exceed ~2-fold the maximum exposure in the single-ascending-dose part.

Group B4 may be dosed concurrently with Group A10 (80 µg), following the dose escalation meeting for Group A9 (40 µg). The predicted C_{max} and AUC_{0-∞} for a single dose of 40 µg are 0.258 ng/mL and 1.673 ng.h/mL, respectively (Table 1). Assuming 3.7-fold accumulation, the predicted C_{max} and AUC_{0-∞} at the 20 µg dose level in Group B4 are 0.294 ng/mL and 3.15 ng.h/mL, respectively (Table 2). Exposure in Group B4, therefore, is not predicted to exceed ~2-fold the maximum exposure in Group A9.

If additional groups (B5 and B6) are required, the predicted systemic exposure will not exceed that stated in the dose escalation stopping criteria [Section 3.7]) based on available PK data.

Details of all doses administered in Parts A and B of the study will be documented in the TMF.

3.6. Dose Escalation

In Part A, doses will be administered in an escalating manner following satisfactory review by the Sponsor and Investigator of the safety, and tolerability data up to Day 10 (216 hours postdose) from groups that received lower doses of OLP-1002. For escalation to doses $\geq 12 \mu\text{g}$, PK data up to Day 7 (144 hours postdose) will also be reviewed. All available safety, tolerability, and PK data from previous groups will be reviewed prior to dose escalation.

In Part B, doses will be administered in an escalating manner following satisfactory review of safety, tolerability, and PK data up to Day 22 (216 hours post-final dose) from groups that received lower doses of OLP-1002. Doses may be reduced and may be lower than the starting dose. Available safety, tolerability, and PK data from all previous groups will be reviewed prior to dose escalation.

Dose escalation in Part A will only occur if data from a minimum of 4 subjects (Groups A1, A3, A5, A7, and A8) or 6 subjects (Groups A2, A4, A6, A9, A10, and A11) have been reviewed from the previous lower dose group, such that data from a minimum of 3 or 4 subjects, respectively, who have received OLP-1002 will be used to make the dose-escalation decision. Dose escalation in Part B will only occur if data from a minimum of 6 subjects have been reviewed from the previous lower dose group, such that data from a minimum of 4 subjects who have received OLP-1002 will be used to make the dose-escalation decision.

The justification for this is as follows:

- The study drug is of a known pharmacological class for which the on-target effects in humans are well characterized. Based upon nonclinical data, no clinically important off-target effects are expected within the proposed dose range.
- A minimum of 3 subjects receiving the active drug is considered sufficient to characterize the safety profile for OLP-1002.

Between each dose escalation, the Investigator will review all available blinded data to ensure it is safe to proceed with the planned dose escalation. An interim safety report, summarizing results from all available safety assessments, will be sent to the Sponsor and a dose-escalation meeting will occur prior to the start of each successive group. Any clinically significant results will be discussed with the Sponsor before dose escalation continues. Interim PD data may also be reviewed on an ongoing basis. In the event of a disagreement between Sponsor and Investigator on the dose-escalation decision, the decision of the Investigator will be upheld.

3.7. Dose Escalation Stopping Criteria

In Parts A and B, following consultation with the Sponsor, dose escalation will be stopped if:

- Clinically relevant signs or symptoms of similar nature occur in 2 or more subjects in a group that, in the opinion of the Investigator, warrant stopping of dose escalation.
- One or more subjects experience an SAE that is considered to be related to OLP-1002.

- Two or more subjects in the same group experience severe non-serious AEs (ie. severe non-serious AEs considered as, at least, possibly related to OLP-1002 administration), independent of whether the AEs are within or not within the same system organ class.
- There is evidence of clinically significant increases in aspartate aminotransferase, alanine aminotransferase or alkaline phosphatase (defined as 3 times the upper limit of normal), or total bilirubin (defined as 2 times the upper limit of normal) that are considered to be related to OLP-1002 in 2 or more subjects in a group. Results will be confirmed with repeat testing.
- QT interval corrected for heart rate using Fridericia's method (QTcF) increases > 60 msec compared to baseline (predose for Part A or Day 1 predose for Part B) and/or absolute QTcF values > 500 msec (confirmed by repeat measurement) in 2 or more subjects in a group.
- Tachycardia (> 150 beats/min) in the resting supine position (confirmed by 2 repeat measurements) on at least 1 occasion within a 24-hour interval in ≥ 1 subject in a group.
- Severe hypertension (systolic blood pressure > 180 mmHg and/or diastolic blood pressure > 110 mmHg) in the resting supine position (confirmed by 2 repeat measurements) on at least 1 occasion within a 24-hour interval in ≥ 1 subject in a group.
- Systemic exposure for any individual subject is predicted to exceed a C_{max} of 24.9 ng/mL (plasma) and/or an AUC_{0-24} of 128 ng.h/mL; i.e., systemic exposure will be no greater than the NOAEL in the most sensitive species (100,000 pmol/kg in rat [462 μ g/kg]).

If the sponsor deems it appropriate to resume dosing after the internal safety review, it can be done after the approval of a substantial protocol amendment.

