4.4. Subject Withdrawal and Replacement

A subject is free to withdraw from the study at any time. In addition, a subject will be withdrawn if any of the following criteria are met:

- noncompliance with the study restrictions that might affect subject safety or study assessments/objectives, as considered applicable by the Investigator (or designee)

- any clinically relevant sign or symptom that, in the opinion of the Investigator (or designee), warrants subject withdrawal, including:
 - a serious adverse reaction (i.e., a SAE considered at least possibly related to OLP-1002 administration),
 - severe non-serious adverse reaction (i.e., severe non-serious AE considered to at least possibly related to OLP-1002 administration),
 - elevated AST, ALT, ALK (3 x ULN) or total bilirubin (2 x ULN),
 - QTcF increases > 60 msec compared to baseline (predose for Part A or Day 1 predose for Part B) and/or absolute QTcF values > 500 msec (confirmed by repeat measurement),
 - Tachycardia (> 150 beats/min) in the resting supine position (confirmed by 2 repeat measurements),
 - Severe hypertension (systolic blood pressure > 180 mmHg and/or diastolic blood pressure > 110 mmHg) in the resting supine position (confirmed by 2 repeat measurements).

If a subject is withdrawn, the Sponsor will be notified and the date and reason(s) for the withdrawal will be documented in the subject's electronic Case Report Form (eCRF). If a subject is withdrawn, efforts will be made to perform all follow-up assessments, if possible ([Appendix 6](#)). Other procedures may be performed at the Investigator's (or designee's) and/or Sponsor's discretion. If the subject is in-house, these procedures should be performed before the subject is discharged from the clinic. The Investigator (or designee) may also request that the subject return for an additional Follow-up visit. All withdrawn subjects will be followed until resolution of all their AEs or until the unresolved AEs are judged by the Investigator (or designee) to have stabilized.

Subjects who are withdrawn for reasons not related to study drug may be replaced following discussion between the Investigator and the Sponsor. Subjects withdrawn as a result of AEs thought to be related to the study drug will generally not be replaced.

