5.4. Blinding

The following controls will be employed to maintain the double-blind status of the study:

- The placebo solution will be identical in appearance to the OLP-1002.
- The Investigator and other members of staff involved with the study will remain blinded to the treatment randomization code during the assembly procedure.

To maintain the blind, the Investigator will be provided with sealed randomization code-break envelopes for each subject, containing details of their treatment. These individual sealed envelopes will be kept in a limited access area that is accessible 24 hours a day. In order to manage subject safety or to support dose-escalation decisions (in the event of possibly treatment-related SAEs or severe AEs), the decision to unblind resides solely with the Investigator. Whenever possible, and providing it does not interfere with or delay any decision in the best interest of the subject, the Investigator will discuss the intended code-break with the Sponsor. If it becomes necessary to break the code during the study, the date, time, and reason will be recorded in the subject's source data and on the individual envelope and will be witnessed by a second person.

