10. APPENDICES

Appendix 1: Adverse Event Reporting

Definitions

An adverse event (AE) is any untoward medical occurrence in a patient or clinical investigation subject administered a pharmaceutical product, which does not necessarily have a causal relationship with this treatment. An AE can therefore be any unfavorable and/or unintended sign (including a clinically significant abnormal laboratory finding), symptom, or disease temporally associated with the use of a study drug, whether or not related to the study drug.

Assessment of Severity

The Investigator will be asked to provide an assessment of the severity of the AE using the following categories:

- **Mild:** Usually transient and may require only minimal treatment or therapeutic intervention. The event does not generally interfere with usual activities of daily living.
- **Moderate:** Usually alleviated with additional specific therapeutic intervention. The event interferes with usual activities of daily living, causing discomfort but posing no significant or permanent risk of harm to the subject.
- **Severe:** Interrupts usual activities of daily living, or significantly affects clinical status, or may require intensive therapeutic intervention.

Relationship to Study Treatment

The Investigator (or designee) will make a determination of the relationship of the AE to the study drug using a 4-category system according to the following guidelines:

- **Not Related:** The AE is definitely caused by the subject's clinical state or the study procedure/conditions.
- **Unlikely Related:** The temporal association between the AE and the drug is such that the drug is not likely to have any reasonable association with the AE.
- **Possibly Related:** The AE follows a reasonable temporal sequence from the time of drug administration but could have been produced by the subject's clinical state or the study procedures/conditions.
- **Related:** The AE follows a reasonable temporal sequence from administration of the drug, abates upon discontinuation of the drug, follows a known or hypothesized cause-effect relationship, and (if appropriate) reappears when the drug is reintroduced.

Follow-up of Adverse Events

Every reasonable effort will be made to follow up with subjects who have AEs. Any subject who has an ongoing AE that is possibly related or related to the investigational medicinal product (IMP) or study procedures at the Follow-up visit will be followed up, where possible,

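### As written, a single possibly related SAE does not trigger the mandatory escalation stop in Section 3.7, although the neighbouring severe-AE rule and Sections 4.4 and 5.4 act at the possibly related level

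*Protocol*

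**What the plan says.** Section 3.7 of the current protocol (Version 5) lists eight criteria that stop dose escalation in Parts A and B. The SAE criterion reads "One or more subjects experience an SAE that is considered to be related to OLP-1002". The criterion after it reads "Two or more subjects in the same group experience severe non-serious AEs" and defines these as "severe non-serious AEs considered as, at least, possibly related to OLP-1002 administration". If the sponsor wishes to resume dosing after a stop, "it can be done after the approval of a substantial protocol amendment".

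Two other sections deal with the same kind of event. Section 4.4 lists among its withdrawal criteria "a serious adverse reaction (i.e., a SAE considered at least possibly related to OLP-1002 administration", and lists severe non-serious reactions at the same causality level. Section 5.4 lets the Investigator break the blind "to support dose-escalation decisions (in the event of possibly treatment-related SAEs or severe AEs".

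Appendix 1 says that the Investigator or designee "will make a determination of the relationship of the AE to the study drug using a 4-category system". The four categories are Not Related, Unlikely Related, Possibly Related and Related.

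**The concern.** The mandatory rule for the more serious class of event asks for stronger evidence of causality than the rule for the less serious class. If the SAE bullet is read against the Appendix 1 scale, an SAE coded Possibly Related stops nothing automatically, and the amendment needed to restart after a stop is never called for. The affected subject can be withdrawn while the next dose group goes ahead.

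This is the first administration of the drug to humans, in healthy volunteers who gain no treatment benefit. Whether escalation halts after a serious event should not depend on how one word is read.

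**Working it through.** There is no figure in the plan to reproduce. The check sets the rules side by side.

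**Step 1. Rules that act on SAEs or severe AEs by causality**

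| Rule | Causality level | Subjects needed |
|---|---|---|
| 3.7, SAE: stop escalation | related | 1, any group |
| 3.7, severe non-serious AE: stop escalation | at least possibly related | 2, same group |
| 4.4, SAE: withdraw subject | at least possibly related | that subject |
| 4.4, severe non-serious AE: withdraw subject | at least possibly related | that subject |
| 5.4, SAE or severe AE: unblinding allowed | possibly related | that subject |

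Four of the five work at the possibly related level. The exception is the mandatory stop for SAEs. That rule is stricter on count (one subject against two), but this does not help if the causality condition is not met.

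**Step 2. What related means.** Appendix 1 defines Possibly Related and Related as distinct categories. Where its follow-up text means both, it names both, also in lower case. A reader who finds different wording in two adjacent bullets of Section 3.7 may reasonably infer two thresholds.

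**Step 3. One subject with an SAE coded Possibly Related, tested against all eight bullets of Section 3.7**

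- SAE bullet: not met on the literal reading.
- Four bullets need at least two subjects in a group: similar clinically relevant signs or symptoms, severe non-serious AEs, liver tests, QTcF. Not met.
- Three bullets can be met by one subject, but only if a measured limit is crossed: pulse rate, blood pressure, predicted exposure. Not met by the SAE alone.

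1 + 4 + 3 = 8, and none is met by that fact alone. The same event satisfies the Section 4.4 withdrawal criterion and falls within the Section 5.4 unblinding provision.

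**Step 4. How readily an SAE could be coded below Related.** The Appendix 1 guideline for Related includes resolution once the drug is stopped. Part A is single-dose (Section 3.1.1), so this cannot be shown there by stopping dosing. A first SAE in Part A may therefore be coded Possibly Related more readily. These are guidelines and the Investigator decides, so this is plausible rather than demonstrated.

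**Step 5. Frequency.** The protocol gives no SAE rate, so the chance that the gap would matter cannot be calculated.

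**The case against.** The strongest objection is that the gap exists only on one reading. Section 3.7 neither cites Appendix 1 nor capitalises the word. Section 4.4 uses it loosely: "Subjects withdrawn as a result of AEs thought to be related to the study drug will generally not be replaced". Appendix 1 defines an adverse drug reaction by a reasonable possibility of causation, and the Amendment 1 log lists the SAE criteria of Sections 3.7 and 4.4 as one addition. All this suggests that a single, broad level may have been intended. It shows that the wording is ambiguous, but not that the bullet is safe as it stands. If one level was meant, the bullet misstates it.

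Second, the four-in-five count leaves out the liver-test bullet, which uses the same wording as the SAE bullet. Among the three causality-based bullets in Section 3.7, two say related. That is correct, and the count should be read as covering SAEs and severe AEs only. It does not explain why a serious event should need stronger causality than a severe non-serious one.

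Third, a two-level design would be coherent: unblind and decide for possibly related events, stop for related ones. Withdrawing one subject is also a smaller step than halting escalation. But the protocol does not describe such a design, and the severe-AE bullet is itself a halt to escalation at the lower level.

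Fourth, other safeguards exist. Section 3.6 requires a satisfactory review and a meeting before each group, with clinically significant results discussed with the Sponsor and the Investigator's decision upheld. Section 3.4.1 leaves dosing of the remaining subjects in a group to the Investigator's discretion, and Section 3.1.2 requires a physician check before each Part B dose. Section 4.5 allows termination, and unexpected serious reactions go to the Ethics Committee and the MHRA. These are real protections and they limit the size of the concern. None is a mandatory stop, and SUSAR reporting is notification, not approval to resume.

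**Conclusion.** The concern holds and should be fixed, with medium confidence. Taken literally, one possibly related SAE meets none of the eight stopping criteria, whereas two possibly related severe non-serious AEs in a group would halt escalation. The conclusion rests on reading the word in Section 3.7 as the Appendix 1 category. The documents do not settle that reading, but they give no reason for a higher level either. Continuing after such an event is not uncontrolled: it rests on judgement rather than on a rule. How often this would arise is unknown.

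**What to change.** Reword the SAE bullet in Section 3.7 so that it applies when one or more subjects have an SAE considered *at least possibly related* to OLP-1002, matching Section 4.4. Add a clause that the criterion is not met if unblinding under Section 5.4 shows that the subject received placebo. The same wording in the liver-test bullet is optional, but it would avoid leaving a lone bullet that invites the strict reading.

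The drafting cost is a few words and one clause. Possibly Related needs little more than a reasonable time sequence, so the stop may fire somewhat more often, and each stop on an active subject requires a substantial amendment before dosing resumes. Because review is blinded, the rule could first fire for a placebo subject; the added clause resolves that at the price of that subject's blind.
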